- 1] allows the stimulation of our proposed list of upper extremity muscles (supraspinatus; infraspinatus; teres major and minor; anterior, middle, or posterior deltoid; biceps; and triceps), which is more than the standard set of muscles (bilateral biceps, triceps and supraspinatus).
- 2] allows to change the timing of the stimulation (On/Off) to produce a smooth cycling motion.

4. FDA approved use description:

The device FDA indication for use are:

1. Relaxation of muscle spasms
2. Prevention or retardation of disuse atrophy
3. Increasing local blood circulation
4. Maintaining or increasing range of motion

5. IDE Info:

Not applicable

c. Study Statistics

1. Primary outcome variable.

Independent Variables

FES or no FES

Dependent Variables: to be measured at 0, 4, 5, 9 and 12months

Severity of gleno-humeral subluxation, measured by X-ray (not measured at 5 months).

Spasticity of the pectoralis, biceps, triceps, and long finger flexor muscles, measured with the Modified Ashworth.

Functional movement of the shoulder, measured with the Capabilities of the Upper Extremity (CUE) test.

Hand function, measured with the Jebsen-Taylor Hand Function (JTHF) and Box and Blocks (BB) tests.

Upper limb function measured with the Action Research Arm test (ARA) test.

Range Of Motion of the upper extremity joints (of the shoulder, elbow, wrist, and fingers/thumbs), measured with goniometry.

Pain, measured with the Numerical Rating Scale (NRS).

Neurological function, measured with the American Spinal Injury Association (ASIA) exam.

2. Secondary outcome variables.

Not applicable

3. Statistical plan including sample size justification and interim data analysis.

Data Analysis: Data will be collected in accordance with each instrument's standardized instructions, with the evaluator being blinded to group assignment. To obtain consistency and facilitate interpretation of the data, we will use means and standard deviations (SDs) to describe normally as well as non-normally distributed variables. Appropriate post-hoc statistical analysis will be used to compare between group means and repeated measures. Baseline tests of homogeneity will be used *a priori*. If statistically significant differences are found after the subjects are randomized to the two groups, they will be corrected in the post-hoc analysis. Results will be considered significant at $P<0.05$.

Power analysis: Because upper extremity, FES-assisted ergometry training is a new intervention, we based our power analysis on previously completed studies that looked at the effect of FES on muscle mass (50, 51) and cardio-vascular conditioning (52-56). A sample size of 24 will allow us to detect a mean difference between the pre- and post-measures. Some of our outcome measures (CUE, JTHF, BB tests) have been shown to respond to many types of rehabilitative interventions, and we believe they will be particularly responsive to the type of training used here. One of our goals is to use the data obtained in this study to determine the magnitude of the effect so we can design future trials. If the magnitude is very small, however, it is unlikely to be clinically relevant. We would then be more likely to propose intensifying the intervention (e.g., by lengthening the periods of cycling) than to suggest increasing sample size.

4. Early stopping rules.

* Subject medical status:

- Requires significant hospitalization (that would interfere with physiologic processes proposed to be studied through the protocol, i.e. e-stim) – at the discretion of PI.
- Increased pain (more than 3 points increase on the NRS).
- Increased shoulder subluxation (more than 1 cm).
- Decreased range of motion (more than 15 deg).

* Subject not compliant:

- Fails to follow directions.
- Become pregnant.

XII. LABELING & STORAGE OF DATA & SPECIMENS

All paper study documents are stored in locked cabinets at the Broadwaycampus of the KKI-ICSCI. Access to the locked cabinets is strictly limited to the study team members listed on this protocol. The documents with identifiers (such as the consent forms, phone screening forms, and the document that links the subject study # to the identity of the subject) are stored in a study binder in a separate locked cabinet from hard copy data collection forms.

All electronic study documents are saved on KKI-ICSCI departmental shared networked drives, and access is strictly limited to the study team members listed on this protocol. The share drives are managed by KKI's Information Systems Department, and housed in a Data Center at KKI's Green Spring Campus. The Data Center is all Card Swipe and Key Pad protected. Access to the Data Center is strictly limited to Director Level and System Administrators. The Data Center is monitored using APC Data Center Monitoring System. We monitor the location with Camera's that store the Video on a Central Server. We monitor the Data Center for Temperature, Humidity and Water as well. All of the Institute's Data is backed to tape on a daily basis and the Tapes are shipped to Iron Mountain, a Data Storage facility. All of the Data on the tapes is encrypted and very secure. All of the Institute Data is also replicated Real Time to our Disaster Recovery site in Baltimore.

All the procedures listed below will be used to protect the confidentiality of data and samples collected and stored for research purposes:

- Only authorized persons will be granted access
- Only authorized persons may enter and view study data
- Passwords and system IDs will not be shared
- Physical security of the workstations/files will be maintained
- Adequate back-up plan is in effect
- Staff trained on data entry system and importance of security procedures
- Workstations with databases will not be left unattended

Authorized persons include:

- the study team members listed on this protocol.
- QA/QI and other regulatory personnel at KKI and the local IRB of Record.

For compliance with 45 CFR 164.528, the local IRB of Record requires investigators to retain study records, along with records of all disclosures of study information, for the following time periods:

- 1) At least 7 years after the last subject has completed his or her participation in the study, or
- 2) The date of the last disclosure of identifiable health information from study records, if disclosures continue after all subjects have completed the study.

Accurate and complete study records will be maintained and made available to representatives of the U.S. Army Medical Research and Materiel Command. These representatives are authorized to review research records as part of their responsibility to protect human research volunteers. Research records will be stored in a confidential manner so as to protect the confidentiality of subject information.

XIII. RISK AND INJURY

a. Risks, Risk Management:

All assessments and intervention sessions will be supervised by the Principal Investigator.

For all the study procedures, the risks and risk management are defined in the sections below.

1. Assessment Risks:

a) Neurological Exam: During testing, the subject might experience pain induced by hitting/tapping of the arm, but usually, the sensation experienced is a quick, non-painful touching sensation. To minimize the risk, one of the study team member trained in the procedure will perform the test.

b) Fast Urine Pregnancy Test: There is the possibility of psychological stress occurring if testing shows that the subject may be pregnant. To minimize the risk in the event that pregnancy test results are positive, the result will be disclosed to the subject. If the subject is uncomfortable with this arrangement, his/her consent to participate in this study is not recommended.

c) Severity of gleno-humeral subluxation: The subjects receive ionizing radiation due to the diagnostic bilateral shoulder X-ray procedures they receive at the Initial, 4th Month, 9th Month, and 12th Month visit. The Total Effective Dose from the procedures is 0.4 rem. This is more than the 0.3 rem that the average person in the United States gets each year from natural sources like the sun, outer space, air, food and soil. It is less than the 5 rems of radiation that is allowed each year for people who are exposed to radiation in their jobs. To minimize the risk, pregnant women are excluded from the study.

d) Spasticity Measurement: There is a risk of eliciting spasms during the test. Subjects will feel a quick pull of the muscle, which might be painful at times. To minimize the risk, one of the study team member trained in the procedure will perform the test.

e) Capabilities of the Upper Extremity (CUE) test: There are no known risks associated with this test.

f) Jebsen-Taylor Hand Function (JTHF) test: Patients may feel some discomfort associated with fatigue in the shoulder, elbow, wrist or hand. To minimize the risk, one of the study team member trained in the procedure will perform the test.

g) Box and Blocks (BB) test: Patients may feel some discomfort associated with fatigue in the shoulder, elbow, wrist or hand. To minimize the risk, one of the study team member trained in the procedure will perform the test.

h) Action Research Arm (ARA) test: Patients may feel some discomfort associated with fatigue in the shoulder, elbow, wrist or hand. To minimize the risk, one of the study team member trained in the procedure will perform the test.

i) Functional Risk (FR) test: Patients may feel anxiety related to loss of balance. To minimize the risk, one of the study team member trained in the procedure will perform the test and will position themselves in the direction of the lean so subject does not fall.

j) Range Of Motion (ROM) of the upper extremity joints: Subjects may feel a stretch near the end range, which could be painful. To minimize the risk, one of the study team member trained in the procedure will perform the test.

k) Numerical Rating Scale (NRS) for pain: There are no known risks associated with this measurement.

l) Pulmonary Function Test (PFTs): The risk is minimal for most people. Since the test involves some forced breathing and rapid breathing, patients may have some temporary shortness of breath or light-headedness. Patients breathe through a tight-fitting mouthpiece, and will have nose clips. To minimize the risk, one of the study team member trained in the procedure will perform the test.

m) American Spinal Injury Association (ASIA) exam: There is a risk of discomfort at the site of the pin prick during the ASIA Exam. To minimize the risk, one of the study team member trained in the procedure will perform the ASIA exam.

n) Pain and Spasticity Medication inventory: Aside from the risk associated with disclosing personnel or protected health information outside the research study, there are no known risks associated with this measurement.

2. *Intervention Risks:*

o) FES: The risk associated with FES is pain at the stimulation site. To minimize the risk, stimulation will only be done to the participant's tolerance level. There is a minimal risk of skin burn. To further **minimize the risk** of skin burn, only appropriate size electrodes will be used and they will be replaced as per the manufacturer's recommendations.

3. *Other Risks:*

p) Time Commitment: The time commitment to the 3 visits per week for 4 months may be inconvenient. To minimize the risk: 1] The subject should contact the study coordinator if having problems scheduling the visits; 2] If we feel that the subject can not commit the time and effort, he/she will be excluded from the study; 3] The visits may cause moderate social, school and work disruption. The start of the study will be scheduled to lessen the disruption.

b. Medical Care For Research Related Injury:

For greater than minimal risk studies, the USAMRMC can commit to providing treatment to research volunteers free of charge in an Army medical facility, therefore the ORP HRPO mandated language shall be included in the consent form.

XIV. BENEFIT(S)

There are no known benefits for those who participate in this study. The possible benefits to the participant from upper extremity FES ergometry include muscle mass and strength increase, muscle tone decrease, cardiovascular conditioning. This study may benefit others in the future by helping understand how upper extremity ergometry with FES might contribute to an improved quality of life for people with cervical spinal cord injuries.

XV. COMPENSATION

a. Payment and Remuneration:

Subjects will be paid a total of \$250.00 if they complete the study. Of this amount, \$20.00 is a bonus, which the subjects will be eligible to receive if they have shown up on time for all study visits as scheduled, and followed the directions of the study staff.

If the subjects do not finish the study, they will be paid only for the amount completed as follows:

\$30.00 for the Initial Visit

\$25.00 for the 1st month of FES treatment

\$25.00 for the 2nd month of FES treatment

\$25.00 for the 3rd month of FES treatment

\$25.00 for the 4th month visit

\$25.00 for the 5th month visit

\$25.00 for the 9th month visit

\$50.00 for the 12th month visit

Payment will be made by check at the final visit.

b. Costs

There is no cost to study participants for any of the study tests. Subjects will be responsible for the cost of travel to and from the Institute (Valet parking is available at no cost to study participant), as well as any food/meals purchased throughout the day while engaged in study procedures.

XVI. CONFIDENTIALITY

All the procedures listed below will be used to protect the confidentiality of data and samples collected and stored for research purposes:

- Only authorized persons will be granted access
- Only authorized persons may enter and view study data
- Passwords and system IDs will not be shared
- Physical security of the workstations/files will be maintained
- Adequate back-up plan is in effect
- Staff trained on data entry system and importance of security procedures
- Workstations with databases will not be left unattended

Accurate and complete study records will be maintained and made available to representatives of the U.S. Army Medical Research and Materiel Command. These representatives are authorized to review research records as part of their responsibility to protect human research volunteers. Research records will be stored in a confidential manner so as to protect the confidentiality of subject information.

XVII. ADVERSE EVENTS

“Unanticipated problems involving risks to participants or others” is defined as:

- The information is unexpected in terms of nature, severity, or frequency, given: a) the research procedures described in the protocol and informed consent document; and b) the characteristics of the subject population being studied; and
- The information indicates that participants or others are at greater risk of harm (including physical, psychological, economic, or social harm) than was previously known or recognized.”

All unanticipated problems involving risk to subjects or others, serious adverse events related to participation in the study and subject deaths related to participation in the study should be promptly reported by [contact]), by email ([contact]), or by [contact]) to the USAMRMC, Office of Research Protections, Human Research Protection Office. A complete written report will follow the initial notification. In addition to the methods above, the complete report will be sent to the U.S. Army Medical Research and Materiel Command, ATTN: MCMR-ZB-PH, [name].

The Medical Monitor is required to review all unanticipated problems involving risk to subjects or others, serious adverse events and all subject deaths associated with the protocol and provide an unbiased written report of the event. At a minimum, the medical monitor must comment on the outcomes of the event or problem and in case of a serious adverse event or death, comment on the relationship to participation in the study. The medical monitor must also indicate whether he/she concurs with the details of the report provided by the principal investigator. Reports for events determined by either the investigator or medical monitor to be possibly or definitely related to participation and reports of events resulting in death must be promptly forwarded to the ORP HRPO.

XVIII. CHANGES TO PROTOCOL

a. Protocol Modifications:

Major modifications to the research protocol and any modifications that could potentially increase risk to subjects must be submitted to the USAMRMC ORP HRPO for approval prior to implementation. All other amendments will be submitted with the continuing review report to the USAMRMC ORP HRPO for acceptance.

b. Protocol Deviations:

Any deviation to the protocol that may have an effect on the safety or rights of the subject or the integrity of the study must be reported to the USAMRMC ORP HRPO as soon as the deviation is identified.

XIX. CONTINUING REVIEW & FINAL REPORT

a. Continuing Review Reports:

A copy of the continuing review report for the research study will be submitted to the local IRB of Record. A copy of the approved continuing review report and the local IRB of Record approval notification must be submitted to the ORP HRPO as soon as these documents become available. PI will report progress of the approved research to the local IRB of Record and the ORP HRPO as often as requested, but not less frequently than once per year.

c. Final Study Report:

A copy of the final study report will be submitted to the local IRB of Record. A copy of the approved/accepted final study report and the local IRB of Record approval/acceptance notification will be submitted to the ORP HRPO as soon as these documents become available.

XX. LITERATURE REVIEW

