Expected Result: An FES paradigm involving ergometry of the upper extremities will enhance subjects' functional recovery, as measured in the clinic by neurological and anatomical indices.

VIII. INCLUSION / EXCLUSION CRITERIA

a. Inclusion criteria:

- a. Male, Female, age 18-55, all ethnic groups.
- b. Spinal Cord Injury, traumatic and non-traumatic.
- c. C1-C6 neurological level.
- d. ASIA class A or B.
- e. Chronic injury,>12 months and < 20 years from the injury.
- f. No upper-extremity electrical stimulation in the previous 4 weeks.
- g. Subjects are medically stable, with no recent (1 month or less) inpatient admission for acute medical or surgical issues.
- h. Baseline physical activity will be kept stable during the study.
- i. Pain and antispasticity medications dose will be kept stable during the study.
- j. Subjects are legally able to make their own health care decisions.

b. Exclusion criteria:

- a. Associated lower motor neuron/peripheral nerve injury in the C1-C6 levels.
- b. Presence of pacemaker.
- c. Presence of cancer.
- d. History of seizures.
- e. Women who are pregnant.

IX. SUBJECT RECRUITMENT & SCREENING**a. Subject recruitment & screening:**Recruitment scenario 1:

Patients of the ICSCI, and prior study participants will be identified as meeting the inclusion criteria by reviewing the medical records held by the ICSCI and filling out a Medical Chart Review Form. A waiver of privacy authorization will be obtained from the local IRB of Record [HIPAA Form4] prior to chart review. Patients will be told about the study during a clinical visit; they will be given a Subject Recruitment Flyer with contact information; a note of this communication will be made in the patient's medical record. Those who are interested can meet privately with, or contact later the principal investigator or study coordinator who will explain in simple terms: 1) the purpose of the research and the procedures involved, 2) potential benefits, 3) potential risks, 4) the subject's right to withdraw at any time without penalty of any sort, and 5) assurance of anonymity. If a patient indicates that he/she is no longer interested or is not eligible, the Medical Chart Review Form will be shredded.

Recruitment scenario 2:

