Subject Recruitment Flyers will be posted at KKI and outside medical facilities who have agreed to do so. Physicians at KKI and these outside facilities will be provided with a guide to inform them generally of the exclusion/inclusion criteria for the study, and extra copies of the flyer to give out to potential subjects. The Subject Recruitment Flyer will be posted on the ICSCI website (www.spinalcordrecovery.org) and 3rd party websites who have agreed to do so. The Study will also be listed on the newsletter published periodically by ICSCI and KKI. The Study will also be listed on KKI Facebook social networking page (<http://www.facebook.com/kennedykrieger>) and other social network sites as appropriate. This study will also be registered on www.clinicaltrials.gov within one year from initial IRB approval. This study can also be posted on and www.centerwatch.com. This study will also be advertised on the KKI on-hold message phone system. This study will be also discussed in a Press Release. All potential subjects who contact us in respond to the recruitment flyers will be called back by the study coordinator to complete a phone screening interview to determine initial eligibility documented in a Phone Screening Form. A waiver of privacy authorization will be obtained from the local IRB of Record [HIPAA Form4] prior to phone screening interview. The study coordinator will explain in simple terms: 1) the purpose of the research and the procedures involved, 2) potential benefits, 3) potential risks, 4) the subject's right to withdraw at any time without penalty of any sort, and 5) assurance of anonymity. If the potential subject is interested in participating, study coordinator will ask the potential subject questions about his/her medical history. The principal investigator or co-investigators will review the potential subject's medical history to ascertain if inclusion criteria are met and that there are no obvious exclusions. The potential subject will be called back to indicate if they are eligible to participate. If a potential subject indicates that he/she is no longer interested or is not eligible, the Phone Screening Form will be shredded.

For all recruitment scenarios:

If the potential subject meets the inclusion criteria and agrees to participate, the subject will receive a copy of the Informed Consent Form. The potential subject will be allowed as much time as needed (up to 1 month) to

Version/Date: 11.0, 16-Sept-2013

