n) Pain and Spasticity Medication inventory: This is a routine exam performed for people with spinal cord injury. Pain and antispasticity medications dose will recorded.

o) FES Evaluation: This is a routine exam performed for people with spinal cord injury prior to receiving FES. Therapist 1 or 6 will test the different muscles that are targeted for this study to achieve the best motor response to FES, and maintain subject comfort. Depending on the neurological level of the subject, the muscles are: supraspinatus; infraspinatus; teres major and minor; anterior, middle, or posterior deltoid; biceps; and triceps.

(2) Intervention:

The subjects will be randomly assigned, in a one-to-one ratio, either to group 1, which will first engage in the FES assisted ergometry followed by the non-FES assisted exercise, or to group 2, which will first engage in the non-FES assisted exercise followed by the FES assisted ergometry.

p) FES Upper Extremity Cycle Ergometry: While undergoing the FES assisted ergometry intervention, the subjects will use an RT300-SLSA upper extremity ergometer configured with FES. Electrode placement will be individually optimized to produce smooth cycling, as measured by crank symmetry, average stimulation level, expended energy per hour, and muscle stiffness. Parameters of stimulation current will also be individually optimized to achieve the best motor response (frequency of 10 to 100 Hz, pulse duration of 50 to 500 μ s, and amplitude of 10 to 140 mA). Silver mesh self-adhesive surface electrodes will be used to conduct the stimulation. They will activate some combination of the following muscles, depending on the neurological level at which they are applied: supraspinatus; infraspinatus; teres major and minor; anterior, middle, or

posterior deltoid; biceps; and triceps. Target cycling speed will be 20 rpm, with a resistance of 0.965Nm. The subjects will warm up between 2 and 10 minutes depending on muscle stiffness or spasms, actively cycle with FES for 1 hour, and cool down of 2 minutes. The ergometer software will be set to provide motor support once muscle fatigue has been reached so the subjects can continue. The subjects will remain seated in their primary wheelchair throughout the treatment. The subjects will cycle for 60 minutes/session, three times a week for 4 months.

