q) Non-FES Upper Extremity Exercise: While undergoing the non-FES exercise intervention, the subjects will receive a specific, individualized exercise regimen, consisting of strengthening, stretching, splinting and any other therapeutic interventions that do not use electrical stimulation.. The subjects will remain seated in their primary wheelchair throughout the treatment. The subjects will exercise for 60 minutes/session, three times a week for 4 months.

2. Study duration and number of study visits required of research participants.

The study will last 12 months. The Study Time Line is found in Figure 1, and the Data Collection Schedule in Table 1.

(1) Assessment:

The following post-consent screening will be performed at the Initial visit:

- a. Neurological Exam (about 30 minutes)
- b. Fast Urine Pregnancy Test (about 15 minutes)

The following assessments will be performed at the Initial Visit:

- o. FES Evaluation (about 15 minutes)

The following assessments will be performed at the Initial, 4th month, 9th month, and 12th month Visits:

- c. Severity of gleno-humeral subluxation (about 30 minutes)

The following assessments will be performed at the Initial, 4th month, 5th month, 9th month, and 12th month Visits:

- d. Spasticity measurement (about 15 minutes)
- e. Capabilities of the Upper Extremity test (about 10 minutes)
- f. Jebsen-Taylor Hand Function test (about 15 minutes)
- g. Box and Blocks test (about 15 minutes)
- h. Action Research Arm test (about 20 minutes)
- i. Functional Reach test (about 5 minutes)
- j. Range Of Motion of the upper extremity joints (about 30 minutes)
- k. Numerical Rating Scale (NRS) for pain (about 1 minutes)
- l. Pulmonary Function Test (PFTs) (about 5 minutes)
- m. American Spinal Injury Association (ASIA) exam (about 60 minutes)
- n. Pain and Spasticity Medication inventory (about 10 minutes)

	Initial	4 th Month	5 th Month	9 th Month	12 th Month	Test Evaluator*	Blinded
	5 hours	4 1/2 hours	3 2/3 hours	4 1/4 hours	4 1/4 hours		
Neurological Exam	√					PI, CoI1	No
Fast Urine Pregnancy	√					N1, N2, N3	No
Shoulder X-Ray	√	√		√	√	PI, CoI3	Yes
Modified Ashworth	√	√	√	√	√	PI, CoI1	Yes
CUE	√	√	√	√	√	T1,T6	Yes
JTHF	√	√	√	√	√	T1,T6	Yes
BB	√	√	√	√	√	T1,T6	Yes
ARA	√	√	√	√	√	T1,T6	Yes
FR	√	√	√	√	√	T1,T6	Yes
ROM	√	√	√	√	√	T1,T6	Yes
Pain NRS	√	√	√	√	√	PI, CoI1, SC2	No
PFTs	√	√	√	√	√	N1, N2, N3	No
ASIA	√	√	√	√	√	PI, CoI1	Yes
Meds Inventory	√	√	√	√	√	PI, CoI1, N1, N2, N3, SC2	No
FES Eval	√					T1,T6	No

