* PI: Principal Investigator, CoI1: Co-Investigator 1, CoI3: Co-Investigator 3, T1-7: Therapist 1-7, N1: Nurse 1, N2: Nurse 2, N3: Nurse 3, SC2: Study Coordinator2.

Table 1: Data Collection Schedule

(2) Intervention:

There are a total of 96 visits: 48 FES assisted intervention visits scheduled 1 hour, 3 times a week for 4 months, and 48 non-FES assisted exercise regimen visits scheduled 1 hour, 3 times a week for 4 months.

3. Blinding, including justification for blinding or not blinding the trial, if applicable.

The evaluator will be blinded to group assignment for the following assessment, but we cannot use true blinding due to the intervention's sensory component:

- c. Severity of gleno-humeral subluxation
- d. Spasticity measurement
- e. Capabilities of the Upper Extremity test
- f. Jebsen-Taylor Hand Function test
- g. Box and Blocks test
- h. Action Research Arm test
- i. Functional Reach test
- j. Range Of Motion of the upper extremity joints
- m. American Spinal Injury Association (ASIA) exam

4. Justification of why participants will not receive routine care or will have current therapy stopped.

All subjects will continue to consistently perform their usual (“baseline”) amount of physical activity throughout the study, including performance of lower extremities assisted FES ergometry, home exercise stretching program, cardiovascular conditioning, etc. “Baseline” activity is defined as amount of physical activity performed for at least 1 month prior to enrollment. Routine care will not be interrupted.

5. Justification for inclusion of a placebo or non-treatment group.

Both groups will receive some type of intervention: upper extremity passive ergometry or FES assisted upper extremity ergometry. This way, the effect of FES application will be extracted.

6. Definition of treatment failure or participant removal criteria.

Treatment failure constitutes of:

- Increased pain (more than 3 points increase on the NRS).
- Increased shoulder subluxation (more than 1 cm).
- Decreased range of motion (more than 15 deg).

Subjects will be removed from the study if they:

- Requires significant hospitalization (that would interfere with physiologic processes proposed to be studied through the protocol, i.e. e-stim) – at the discretion of PI.
- Become pregnant.

7. Description of what happens to participants receiving therapy when study ends or if a participant's participation in the study ends prematurely.

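### Inclusion criterion i sets no stable-dose period before entry for pain and antispasticity drugs, so a recent dose change can add noise to the month-0 Modified Ashworth and pain NRS

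*Combined protocol and SAP*

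**What the plan says.** Section VIII.a, criterion i: "Pain and antispasticity medications dose will be kept stable during the study". The requirement runs forward from entry only.

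Other entry conditions in the same protocol look back:

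- Criterion f: "No upper-extremity electrical stimulation in the previous 4 weeks".
- Criterion g, on medical stability: "with no recent (1 month or less) inpatient admission for acute medical or surgical issues".
- Criterion h asks for stable physical activity on study, in wording parallel to criterion i. Section XI.a.4 then supplies its baseline: "amount of physical activity performed for at least 1 month prior to enrollment".

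Section XI.c.1 lists among the dependent variables "Spasticity of the pectoralis, biceps, triceps, and long finger flexor muscles, measured with the Modified Ashworth", and also pain on the NRS. Both are first measured at the Initial visit (section XI.a.2, Table 1).

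For the drugs themselves, section XI.a.1, item n, says only "Pain and antispasticity medications dose will recorded". Section XI.a.2 schedules this inventory at all five visits.

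**The concern.** Antispasticity and pain drugs are given to change what the Modified Ashworth and the NRS measure. If a dose has just been changed, part of its effect may still be developing when month 0 is recorded. The change from month 0 to month 4 then mixes the intervention with the drug's settling. Criterion i already keeps out a candidate who is still titrating, since that dose could not be held. It does not keep out someone who completed a change shortly before the Initial visit and then holds the new dose.

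At stake is precision on two listed dependent variables in a trial of 24 subjects. The remedy belongs at entry, because it decides who enters and when.

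**Working it through.** **1. Entry conditions side by side**

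| Condition | Stable on study? | Look-back before entry |
|---|---|---|
| f, arm stimulation | not stated | 4 weeks |
| g, medical stability | not stated | 1 month, inpatient admissions only |
| h, physical activity | yes | at least 1 month (XI.a.4) |
| i, pain and antispasticity dose | yes | none |

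Criterion g does not fill the gap, because an outpatient dose change involves no admission. The medical-history review in section IX.a checks candidates against these same criteria. The screening forms listed in the appendix are not shown, so what they ask is unknown.

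**2. Which readings are exposed**

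Visits are at months 0, 4, 5, 9 and 12. The documents give no settling time for a dose change, so call it S and treat it as an assumption.

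- S about 1 month: only the month-0 reading can be unsettled. The month-4 reading comes at least 4 months after the change.
- S between 1 and 4 months: still only month 0, but a 1-month window would reduce the problem without removing it.
- S above 4 months: month 4 and later readings could also be affected. Nothing in the documents suggests this.

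Under the first two cases:

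- First-period change (month 4 minus month 0): exposed.
- Any other change measured from month 0: exposed through the same reading.
- Second-period change (month 9 minus month 5): not exposed.
- Within-subject contrast of month 4 with month 9: not exposed, since it does not use month 0.

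Section XI.c.3 does not fix which contrasts will be analysed. Its sample-size paragraph speaks of pre- and post-measures, so change from month 0 is a likely one.

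**3. Noise or bias**

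Let δ be the unsettled part of a recent changer's month-0 score, taken as equal across such subjects for simplicity. Let k1 and k2 be the numbers of recent changers in the two groups of 12. The between-group difference in mean first-period change shifts in size by

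|k1 − k2| × δ / 12.

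Randomisation makes the expected value of k1 − k2 zero, so this is noise in the comparison. For a chance excess of one changer the shift is δ/12 = 0.083δ; for two, 2δ/12 = 0.167δ; for three, 3δ/12 = 0.25δ. Neither δ nor the number of recent changers is in the documents. These lines show scale only and do not estimate the effect.

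**The case against.** The strongest reply is that little is left once the safeguards are counted. Subjects are more than 12 months from injury and medically stable, anyone still titrating is already excluded, allocation is randomised, and no document shows that a recent changer will present. The crossover helps further: month 5 gives a new baseline, and month 4 against month 9 avoids month 0 altogether. All of this stands, and it limits the point to the month-0 reading and changes measured from it. It does not explain why the dose criterion alone among these conditions lacks a look-back.

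The reply on cost also has force. Section IX.a grants decision time ("The potential subject will be allowed as much time as needed (up to 1 month) to" decide) only to a candidate who already meets the inclusion criteria, and screening forms of ineligible candidates are shredded. A bare 1-month rule could therefore lose a recent changer who needed only to wait. The fix has to deal with this.

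Three stronger readings are tempting, and the documents do not support them:

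- A reader might infer that the treatment comparison is biased. A change made before randomisation is not related to group except by chance.
- A reader might infer from the leg-cycling experience in section VII.a, where most FES subjects reduced or simplified antispasticity treatment, that doses will move here too. That was a different intervention, the text does not say whether doses were meant to be held, and criterion i requires stability in this trial. It supplies no rate.
- A reader might count the five-visit inventory as a defect because no analysis use is stated. Checking compliance with criterion i is its obvious purpose, and its absence from section XI.c is missing detail in a short analysis section. The number of inventories taken measures no harm.

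**Conclusion.** The concern holds as a minor design point. Criterion i has no stable-dose period before entry, and a subject with a recent, completed dose change qualifies. The consequence is avoidable noise in the month-0 Modified Ashworth and NRS and in the first-period change from baseline.

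Its size cannot be derived. On the simple model above, each chance excess of one recent changer moves the first-period group difference by one twelfth of that subject's unsettled effect. The conclusion assumes that some recent changers would present, that drug effects settle within about a month (the limit to month 0 holds up to about 4 months), and that change from month 0 is among the contrasts analysed. It does not extend to bias in the treatment comparison, or to the second-period change and the month 4 against month 9 contrast.

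**What to change.** Amend criterion i to read: *pain and antispasticity medication dose unchanged for at least 1 month before the Initial visit and kept stable during the study*. Add that the window is judged at the date of the Initial visit, so that a recent changer found at chart review or phone screening is given a later visit and is not discarded as ineligible. The 1-month length follows the protocol's own standard in criterion g and section XI.a.4.

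The cost is one reworded criterion, one scheduling instruction, and a wait of up to a month for a few candidates. With the window judged prospectively, part or all of that wait can overlap the decision time in section IX.a. No visit, test or model is added.

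Optionally, the report could tabulate on-study dose changes from the existing inventory beside the Ashworth and NRS results. That is a reporting suggestion, and the amendment does not depend on it.
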